### 5.7.3. Safety related Stopping criteria for an individual subject

A subject may be withdrawn from the study if they present dose limiting toxicity (as defined in Section 5.5.1; also refer to tolerability assessment definition in Section 6.3.4.1.). If dose limiting toxicity is observed in an individual, the Investigator or designee may use their medical judgment and stop dosing the individual subject, and is required to immediately inform the GSK medical monitor or designee. They will then decide whether it is necessary for the SMC to be convened immediately or not, for review of the data and decision on dose adjustment or withdrawal of the individual subject.

A subject may be withdrawn from the study if they present a Serious Adverse Event (SAE), regardless of its severity, and reasonably attributable in the opinion of the investigator to dosing with GSK2646264.

A subject will be withdrawn if they require concomitant medications listed in Section 5.15.

Dosing to an individual may be stopped due to unacceptable local tolerability as evidenced by dose limiting toxicity (as defined in Section 5.5.1).

Tolerability assessments on treated skin areas will be made using the criteria in Section 6.3.4.1.

In the presence of any of the above events, every effort will be made to take a blood sample at the time of the event for pharmacokinetics analysis.

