13. A positive drug screen at screening or Day -1 (parts A & B only). For Part B patients, a positive drug screen due to concomitant medication may be acceptable for inclusion in the study based on the Investigator's opinion. The Investigator's opinion must be based on interview of the subject, documented in the medical history and the Investigator is asked to document that the positive test can be explained by a relevant and permitted medication (see Section 5.15.1.) and that the medication will not interfere with the study procedures or compromise subject safety. A drug screen will not be performed in Part C.
14. Lactating females.
15. Where participation in the study would result in donation of blood or blood products in excess of 500 mL within a 56 day period.
16. The subject has participated in a clinical trial and has received an investigational product within the following time period prior to the first dosing day in the current study: 30 days, 5 half-lives or twice the duration of the biological effect of the investigational product (whichever is longer).
17. Exposure to more than four new chemical entities within 12 months prior to the first dosing day
18. Use of topical steroids or calcinurin inhibitors is prohibited during the study from screening to follow up (See Section 5.12).
19. Exclusion related to prior drug treatments:
  - a) Intake of oral corticosteroids within 7 days >10mg/day prior to first screening visit.
  - b) Use of depot corticosteroids within 7 days prior to first screening visit.
  - c) Subjects who are taking anticoagulants (e.g. warfarin) must not be on warfarin within 21 days prior to screening. (See Section 5.15).
  - d) Subjects who are having psoralen combined with ultraviolet A (PUVA) treatment must not be using PUVA treatment within 21 days prior to screening.

20. Subjects who work for the Sponsor, Contract Research Organisation (CRO), or one of the study centres.

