### **5.15.1. Permitted Medications**

#### **5.15.1.1. Parts A, B and C**

Paracetamol, at doses of up to 2 grams/day is permitted for use any time during the study.

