#### **5.15.1.2. Part C only**

Any non-sedating, short-acting antihistamine at licensed dose is permitted for use as rescue medication any time during the study.

Other concomitant medication may be considered on a case by case basis by the investigator in consultation with the GSK Medical monitor if required.

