### 5.15.2. Prohibited Medications and Non-Drug Therapies

Subjects must abstain from taking prescription or non-prescription drugs (including vitamins and dietary or herbal supplements), within 7 days (or 14 days if the drug is a potential enzyme inducer), or 5 half-lives (whichever is longer or as specified in the inclusion / exclusion Section 4.1), or as indicated for specific medications, from screening until completion of the follow-up visit, unless in the opinion of the Investigator and sponsor if required, the medication will not interfere with the study, in which case the investigator is required to document the rationale for their opinion.

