**Table 9 List of Prohibited Medications and Non-Drug Therapies**

Medication	Examples
Use of anticoagulants	e.g. warfarin
Use of systemic immunosuppressants/immunomodulators	e.g. ciclosporin A, dapsone, methotrexate, mycophenolate, chloroquine, and comparable drugs
Use of oral, depot, or topical corticosteroids	e.g. prednisolone
Use of topical calcinurin inhibitors	e.g. tacrolimus, pimecrolimus
Use of tricyclic antidepressants with antihistaminergic properties	e.g. doxepin
Use of UV therapy	including PUVA.
Use of Ketotifen,	
Use of H2 antihistamines	e.g. ranitidine, cimetadine
Use of Leukotriene antagonists	e.g. montelukast
Part A and Part B only: Use of H1 antihistamines	e.g. cetirizine, loratadine
Part C Use of H1 antihistamines above the licensed dose	e.g. cetirizine, loratadine

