11.1.2. Exclusions from Per Protocol Population

A subject meeting any of the following criteria will be excluded from the Per Protocol population:

Number	Exclusion Description
01	
• Failure of any inclusion/exclusion criteria
02	
• Subjects who developed the withdrawal criteria but were not withdrawn
03	
• Any deviation that impact the safety of subjects
04	
• Failed to provide scheduled assessment
05	
• Major deviation from the conduct of trial

Protocol deviation definition criteria and resulting exclusion from analysis populations will be agreed and summarized in a separate protocol deviation definition document that has to be updated and reviewed on a regular basis.

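### Protocol 5.7.3 makes withdrawal mandatory for drugs listed in Section 5.15, but that section also lists drugs the plan permits, including the Part C rescue antihistamine

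*Protocol*

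**What the plan says.** **Withdrawal rule.** Protocol 5.7.3: "A subject will be withdrawn if they require concomitant medications listed in Section 5.15". The wording is mandatory, whereas dose-limiting toxicity and drug-related serious adverse events in the same section only allow withdrawal.

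**Permitted drugs inside Section 5.15.** For all parts, 5.15.1.1: "Paracetamol, at doses of up to 2 grams/day is permitted for use any time during the study". For Part C, 5.15.1.2: "Any non-sedating, short-acting antihistamine at licensed dose is permitted for use as rescue medication any time during the study".

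**Prohibited drugs inside Section 5.15.** Table 9 bars, in Part C, "Use of H1 antihistamines above the licensed dose". For all parts it bars "Use of oral, depot, or topical corticosteroids", with no dose threshold. Section 5.15.2 applies the ban "from screening until completion of the follow-up visit", subject to an exception where the investigator (and the sponsor if required) judges that the drug will not interfere and the rationale is documented.

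**Entry criterion on oral steroids.** Exclusion 19a in Protocol 4.2.2: "Intake of oral corticosteroids within 7 days >10mg/day prior to first screening visit".

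**Per-protocol set.** SAP 11.1.2, item 02, excludes "Subjects who developed the withdrawal criteria but were not withdrawn".

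**The concern.** A withdrawal rule has to tell a site, without interpretation, who leaves. Here one section permits a drug at any time and another requires withdrawal of a subject who needs it. A site cannot follow both.

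In Part C the drug concerned is rescue for the disease under study. The diary in Protocol Appendix 3 offers many wheals with severe pruritus, or angioedema, as reasons for antihistamine intake. Losses under the literal rule would therefore be linked to disease activity and could be informative for UAS7, AAS and DLQI. Early withdrawal would also put at risk the later PK, CD69 and thyroid samples on Days 10, 15 and 22, because Protocol 4.5 sets no schedule for subjects after withdrawal.

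**Working it through.** The plan gives no precision or power figure for Part C, so there is none to reproduce. The check sets the passages side by side and then sizes the consequence.

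**1. Scope of the cross-reference**

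| Medication | Where | Status there | 5.7.3 as written |
|---|---|---|---|
| Paracetamol up to 2 g/day, all parts | 5.15.1.1 | permitted | withdraw |
| Short-acting antihistamine, licensed dose, Part C | 5.15.1.2 | permitted as rescue | withdraw |
| H1 antihistamine above licensed dose, Part C | Table 9 | prohibited | withdraw |
| Oral corticosteroid, any dose | 5.15.2, Table 9 | prohibited, documented exception possible | withdraw, no exception |

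The first two rows are contradictions. In the fourth, the exception in 5.15.2 has no counterpart in 5.7.3.

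**2. What withdrawal costs in Part C**

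Inputs: Protocol 6.1.4 and 6.5.2.2 (post-dose diary days 2 to 8, completed before dosing on dosing days); 9.3.2.3.2 and SAP 11.5.2 (UAS7 needs at least 4 of 7 daily scores and is otherwise missing; AAS is a 7-day total with no imputation); 6.6.1 (post-dose DLQI on Day 8 only).

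A subject who leaves on Day d after completing that day's diary has d − 1 post-dose entries.

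- Day 4: 4 − 1 = 3, below 4, so UAS7 is missing.
- Day 5: 5 − 1 = 4, so UAS7 is prorated (sum × 7/4).
- Any day before Day 8: no post-dose DLQI and an incomplete AAS week.

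The SAP's time-and-events table follows Amendment 2 and runs the diary over Days 1 to 7. Counted that way, the UAS7 limit moves one day earlier; the DLQI and AAS losses then apply before Day 7.

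**3. Size of a loss**

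Inputs: 16 subjects at 3:1 (Protocol 3.1.5, 5.4); withdrawn subjects not replaced (SAP 11.5.1).

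- Active 16 × 3/4 = 12; placebo 16 × 1/4 = 4. One placebo subject is 1/4 = 25% of the controls.
- 95% CI half-width for the SAP's ANCOVA (treatment plus baseline), in residual SDs: t(0.975; n1 + n2 − 3) × √(1/n1 + 1/n2).

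| Active vs placebo | Half-width | Ratio to 12 vs 4 |
|---|---|---|
| 12 vs 4 | 1.25 | 1.00 |
| 11 vs 3 | 1.43 | 1.15 |
| 9 vs 3 | 1.51 | 1.21 |
| 6 vs 2 | 2.10 | 1.68 |

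**4. How many subjects**

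The documents give no rescue rate. As an assumption, take a common rate p of 10% to 50% in both arms, with no treatment difference built in. Expected number is 16p; chance of at least one is 1 − (1 − p)^16; chance that at least two of the four placebo subjects are affected is 1 − (1 − p)^4 − 4p(1 − p)^3.

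| p | Expected of 16 | At least one | Two or more of 4 placebo |
|---|---|---|---|
| 10% | 1.6 | 81.5% | 5% |
| 20% | 3.2 | 97.2% | 18% |
| 30% | 4.8 | 99.7% | 35% |
| 50% | 8.0 | >99.9% | 69% |

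These are counts of subjects who would meet the literal rule, not forecasts of withdrawals.

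**5. If the subject is kept in**

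Item 02 of SAP 11.1.2 then applies and the subject leaves the per-protocol set. SAP 9.1.1 names that set alongside the PD set, but SAP Section 4 uses it only as required. In SAP 11.10.10 and 11.10.11, Tables 5.1 to 5.16 and Figures 5.1 to 5.15 are all assigned to the PD population, so no listed PD display changes.

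**6. Oral corticosteroids**

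Exclusion 19a looks at the 7 days before the first screening visit and bars only more than 10 mg/day. Table 9 applies from screening onward at any dose. A subject on 10 mg/day or less who stops by screening satisfies both. The provisions fail to align only for a subject who enters on such a dose and still needs it.

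**The case against.** The strongest reply is that the target of the cross-reference is plain from context. Rescue is permitted at any time, Table 9 bars H1 antihistamines in Part C only above the licensed dose, the diary records antihistamine intake with no withdrawal instruction, and the literal reading would also withdraw anyone needing paracetamol. On that view this is loose drafting that sites would be unlikely to apply. This stands as evidence about intent, and a reader should not infer that rescue users will in practice be withdrawn. It does not remove the contradiction: the rule is mandatory, it names the whole section, and Protocol 4.2 does not allow waivers except for immediate safety concerns.

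Several stronger inferences are tempting but unsupported.

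- **Bias toward no difference.** This needs more rescue use on placebo than on active. No rate by arm is given, and the available data of withdrawn subjects stay in the summaries (SAP 11.5.1). The direction is unknown.
- **Per-protocol exclusion distorting the PD results.** No listed PD display uses that set.
- **A direct steroid contradiction.** The two rules cover different windows and 5.15.2 has an exception. Steroid use at entry is also not disease behaviour on study.
- **A disturbed UAS7 baseline.** Screening runs from Day −28 to Day −7, so stopping at screening falls before the seven diary days or, at the latest, on the first of them.

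The quoted sentence does not say whether withdrawal is from treatment or from the study. Neighbouring sentences say the study, and the data losses above assume that.

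**Conclusion.** Wrong as written: an internal inconsistency of moderate severity. Section 5.7.3 cannot be followed together with 5.15.1.

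If it is applied literally, the cost is exploratory Part C data, and it is sharp only because there are four controls. The missing-score consequences follow from the documents' own rules. How many subjects are affected does not: it rests on an assumed rescue rate. The half-widths assume the SAP's ANCOVA with one covariate.

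The study tests no formal hypothesis and its sample size rests on feasibility. The safety population is anyone who received a dose, so its membership is unaffected, although follow-up of a withdrawn subject could be shorter. The steroid mismatch is real but secondary, confined to a subject who enters on a lower dose and continues to need it.

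**What to change.** The sponsor should:

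1. Reconcile Protocol 5.7.3 with 5.15.1 and with 5.15.2/Table 9, so that each medication is either permitted or a withdrawal trigger and not both. State whether withdrawal means from treatment or from the study, and whether the documented exception in 5.15.2 carries over to 5.7.3.
2. Reconcile exclusion 19a with Table 9 for oral corticosteroids, in both dose and time window.
3. Make item 02 of SAP 11.1.2 consistent with the outcome, saying explicitly how permitted rescue use is treated.

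Which medication and withdrawal rule applies is for the sponsor to decide; this review takes no view. The cost is a few sentences in the protocol and one in the SAP, with no added visits, data or patients.

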### 5.8. Dose Adjustment/Stopping Pharmacokinetic Criteria

Available pharmacokinetic, safety and tolerability data for at least 6 subjects in Part A, and 4 subjects in Part B following administration of each dose will be reviewed prior to progressing to the subsequent dose group or cohort in the study as described in Section 5.5.2 and Section 5.5.3. The decision to proceed will be made by the Principal Investigator/ Physician designee together with the Medical monitor following discussion

at the SMC. If deemed necessary at any time, the dose escalation will be temporarily halted and no further subject will be dosed and/or the planned number of doses of study medication received by a subject and/or amount of dose applied may be adjusted as appropriate to be lower or higher than currently proposed.

After the first 4 subjects in Part C, available pharmacokinetic data may be reviewed by the sponsor (see Section 5.5.3.4). If required, a discussion with the SMC regarding any changes or adjustments to the dosing regimen in Part C will be held.

#### **5.8.1. Adjusting dose/ stopping dose escalation**

If (cohort's average) predicted or observed  $C_{max}$  or  $AUC(0-24\text{ h after last dose})$  of GSK264624 is greater than 16 ng/mL or 220 ng.hr/mL, respectively, doses for subsequent cohorts may be adjusted based on tox cover and will need to be decided by the SMC but will not exceed agreed margins.

#### **5.9. Blinding**

This will be a randomised double blind (sponsor unblinded), single, bilateral (Part A) and parallel (Parts B and C) repeat ascending dose First Time in Human study in healthy subjects, cold urticaria and chronic spontaneous urticaria subjects study.

The investigator or treating physician may unblind a subject's treatment assignment **only in the case of an emergency**, or in the event of a serious medical condition when knowledge of the study treatment is essential for the appropriate clinical management or welfare of the subject as judged by the investigator. Investigators have direct access to the subject's individual study treatment. It is preferred (but not required) that the investigator first contact the GSK Medical monitor or appropriate GSK study personnel to discuss options **before** unblinding the subject's treatment assignment. If GSK personnel are not contacted before the unblinding, the investigator must notify GSK as soon as possible after unblinding, but without revealing the treatment assignment of the unblinded subject, unless that information is important for the safety of subjects currently in the study. The date and reason for the unblinding must be fully documented in the appropriate data collection tool.

A subject will be withdrawn if the subject's treatment code is unblinded by the investigator or treating physician. The primary reason for discontinuation (the event or condition which led to the unblinding) will be recorded in the eCRF.

GSK's Global Clinical Safety and Pharmacovigilance (GCSP) staff may unblind the treatment assignment for any subject with an SAE. If the SAE requires that an expedited regulatory report be sent to one or more regulatory agencies, a copy of the report, identifying the subject's treatment assignment, may be sent to clinical investigators in accordance with local regulations and/or GSK policy.

#### **5.10. Packaging and Labelling**

The contents of the label and the packaging will be in accordance with all applicable regulatory requirements.

## **5.11. Preparation/Handling/Storage/Accountability**

A description of the methods and materials required for preparation of GSK2646264 is given below. More details will be available for sites to use in the SPM. All bottles are for single use only.

### **5.11.1. Part A and Part B**

Study treatment must be dispensed or administered according to procedures described herein. Only subjects enrolled in the study may receive study treatment. Only authorised site staff may supply or administer study treatment. All study treatment must be stored in a secure area with access limited to the investigator and authorized site staff. Study treatment is to be stored at 2-8°C and protected from light. Maintenance of a temperature log (manual or automated) is required.

### **5.11.2. Part C**

Study treatment must be dispensed or administered according to procedures described herein. Only subjects enrolled in the study may receive study treatment. Only authorised site staff may supply or administer study treatment. All study treatment must be stored in a secure area with access limited to authorized staff. Study treatment is to be stored at 2-8°C and protected from light. Maintenance of a temperature log (manual or automated) is required.

The investigator, institution, or the head of the medical institution (where applicable) is responsible for study treatment accountability, reconciliation, and record maintenance. The investigator or the head of the medical institution (where applicable), or designated site staff (e.g., storage manager, where applicable) must maintain study treatment accountability records throughout the course of the study. The responsible person(s) will document the amount of study treatment received from and returned to GSK and the amount supplied and/or administered to and/or returned by subjects. The required accountability unit for this study will be a bottle. Discrepancies are to be reconciled or resolved. Procedures for final disposition of unused study treatment are listed in the SPM.

Investigational product is not expected to pose significant occupational safety risk to site staff under normal conditions of use and administration. Gloves should be used during the application of this product to the body. Take adequate precautions to avoid direct eye or skin contact and the generation of aerosols or mists. In the case of unintentional occupational exposure notify the monitor, medical monitor and/or study manager. A Material Safety Data Sheet (MSDS)/equivalent document describing occupational hazards and recommended handling precautions either will be provided to the investigator, where this is required by local laws, or is available upon request from GSK.

Precaution will be taken to avoid direct contact with the investigational product. A Material Safety Data Sheet (MSDS) describing occupational hazards and recommended handling precautions will be provided to the investigator for the API (GSK2646264).

The formulation used in this study has been developed specifically for assessment in the FTIH and is unlikely to be the final formulation.

## **5.12. Assessment of Compliance**

When subjects are dosed at the study unit, they will receive study treatment directly from the investigator or designee, under medical supervision. The date and start and end times of each dose administration in the clinic will be recorded in the source documents and transcribed into the InForm eCRF. The dose of study treatment and study participant identification will be confirmed at the time of dosing by a member of the study site staff other than the person administering the study treatment.

## **5.13. Treatment of Study Treatment Overdose**

For this study, any dose of GSK2646264 that is above that intended dose is considered an overdose.

GSK does not recommend specific treatment for an overdose. The investigator or physician in charge of the subject at the time will use clinical judgment to treat any overdose.

## **5.14. Treatment after the End of the Study**

Subjects will not receive any additional treatment from GSK after completion of the study because OR the indication being studied is not life threatening or seriously debilitating and/or other treatment options are available.

The investigator is responsible for ensuring that consideration has been given to the post-study care of the patient's medical condition, whether or not GSK is providing specific post-study treatment.

## **5.15. Concomitant Medications and Non-Drug Therapies**

Concomitant medication must be recorded (as detailed in the SPM).

### **5.15.1. Permitted Medications**

#### **5.15.1.1. Parts A, B and C**

Paracetamol, at doses of up to 2 grams/day is permitted for use any time during the study.

#### **5.15.1.2. Part C only**

Any non-sedating, short-acting antihistamine at licensed dose is permitted for use as rescue medication any time during the study.

Other concomitant medication may be considered on a case by case basis by the investigator in consultation with the GSK Medical monitor if required.

### 5.15.2. Prohibited Medications and Non-Drug Therapies

Subjects must abstain from taking prescription or non-prescription drugs (including vitamins and dietary or herbal supplements), within 7 days (or 14 days if the drug is a potential enzyme inducer), or 5 half-lives (whichever is longer or as specified in the inclusion / exclusion Section 4.1), or as indicated for specific medications, from screening until completion of the follow-up visit, unless in the opinion of the Investigator and sponsor if required, the medication will not interfere with the study, in which case the investigator is required to document the rationale for their opinion.

